## **Withdrawal from the study**

Patients withdrawn from study due to a protocol violation will be included in the safety database of the study. Patients withdrawn from study because their initial TB isolate is found to be MDR –TB will not be followed up further, unless required for patient safety (e.g. an adverse event present, in which case follow-up should occur as clinically indicated). Similarly, patients withdrawn from study because their initial cultures are negative do not need to be followed up further (unless there is an ongoing adverse event). Participation in the study is strictly voluntary. A participant has the right to withdraw from the study at any time for any reason. Patients who withdraw their consent will not have to undergo any follow up procedures.

This study will be reviewed by a Safety Monitoring Committee (SMC) that meets for scheduled reviews of studies every year. A full SMC review will include an efficacy review and a futility review for detecting a survival difference. A full review will be scheduled at least annually after opening to accrual or on a frequency determined by the SMC. For each full review, summaries provided to the SMC will be broken down by treatment arm. Participants' baseline demographic and health characteristics will be summarized. Review of study conduct will address site accrual, premature study discontinuations and their reasons (administrative or loss to follow-up), tracking of potential losses to follow-up, data completeness. The SMC will also review participants' safety data, frequency and causes of death, as well as incidence of TB recurrence.

In addition, quarterly internal reviews of patient charts, SAE reports and regulatory submissions will be conducted.

## **9.0 STATISTICAL CONSIDERATIONS**

### **9.1 Sample size determination:**

A total of 330 patients will be enrolled. A two group continuity corrected chi square test with a 0.05 two-sided significance level will have 80% power to detect the difference between 75% of patients having culture conversion in the Intervention arm and 60% of patients having culture conversion in the Control arm. A previous unpublished retrospective review at the study site comparing the treatment outcome in retreatment

patients with TB using the standard 4 drug regimen, showed a cure and completion rate of 60.1%. According to WHO surveillance data, the retreatment regimen is successful in about 70% of patients, and other retrospective studies show treatment success rates of 26 – 92%. Thus, 75% is a realistic cure and completion rate to aim for in the Intervention group. A previous unpublished retrospective review at the study site comparing the treatment outcome in retreatment patients with TB using the standard 4 drug regimen, showed a cure and completion rate of 60.1%. According to WHO surveillance data, the retreatment regimen is successful in about 70% of patients, and other retrospective studies show treatment success rates of 26 – 92%. Thus, 75% is a realistic cure and completion rate to aim for in the Intervention group.

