## 1.0 INTRODUCTION

### 1.1 Background

South Africa has the worst co-epidemic of tuberculosis (TB) and Human Immunodeficiency Virus (HIV) in the world where an estimated 70% of TB patients are co-infected with HIV. The dual epidemics have led to unacceptably high TB recurrence rates and previous TB treatment is a strong determinant of drug resistance. In 2010, patients with previously treated tuberculosis comprised 15% of global TB notifications. South Africa has the fourth highest number of multi-drug resistant TB (MDR TB) cases and the proportion of MDR TB was five times higher in those with previously treated TB. According to the World Health Organization (WHO), an estimated 53% of retreatment TB cases were co-infected with HIV in 2011 with only 54% of these patients receiving concomitant ART. In order to reduce the risk of recurrent TB, both the cure rate and the case detection rate need to be improved. In South Africa the treatment interruption rate on the standard WHO retreatment regimen is 12%. This non-adherence to the retreatment regimen likely contributes to the increasing burden of MDR TB. There is a critical need for an evidence-based retreatment regimen to improve treatment outcomes of recurrent TB, a regimen that can reduce morbidity and mortality in a shorter time period. The translation of these findings to the clinical setting is urgently required as it has the potential to change current retreatment protocols which are protracted with low success rates.

The existing World Health Organization Standardized Category II Retreatment Regimen (WSRR), adds a single injectable drug, streptomycin, to the first line 4 drug TB treatment regimen (RHZE) in the intensive phase. This regimen, used to treat 1 million patients each year, was based on expert opinion, and has yet to be tested in a randomized controlled clinical trial. Previous studies of the WSRR include a systematic review, a meta-analysis and a prospective cohort study. The systematic review, of published evidence of treatment of patients with a history of previous treatment or documented Isoniazid mono-resistance, included 33 trials, showed that in 1,907 patients lower failure, relapse, and drug resistance were associated with longer duration of Rifampicin, daily treatment and the use of a greater number of effective drugs.

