## **9.2 Analysis including statistical methods**

To answer the primary objective of this study the sputum culture conversion rates at the end of the intensive phase and at month 6 will be compared between the two treatment arms. This will be done by calculating the proportion of culture conversions in each of the two arms and comparing these using the chi-square test.

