## 2. STUDY DESIGN

This is an open label randomized controlled clinical trial comparing two regimens for treatment of smear-positive pulmonary TB, among patients previously treated for TB. The primary objective is to determine if a Moxifloxacin-containing regimen, substituting Moxifloxacin for Ethambutol, of 24 weeks duration is superior to a control regimen of 24 weeks duration in improving treatment outcomes in patients with recurrent TB.

This study will include adults 18 years and over with a previous history of TB. HIV infected and uninfected patients will be included in the study as well as patients on ARVs provided that these are not contra-indicated with any of the study drugs. Patients with M tuberculosis

resistance to Rifampicin will be excluded at screening using Gene Xpert technology. A maximum of 330 participants will be included in the study.

Patients will be randomized in a 1:1 ratio to receive one of the two TB retreatment regimens, as outlined in the table below.

|                         | Intensive Phase (2 months) | Continuation Phase |
|-------------------------|-----------------------------------|---------------------------|
| Intervention Arm | HRZM* daily (2 months)            | HRM* daily (4 months)     |
| Control Arm      | HRZE* daily (2 months)            | HR* daily (4 months)      |

\* Isoniazid (H), Rifampicin (R), Pyrazinamide (Z), Moxifloxacin (M), Ethambutol (E)

The duration of TB treatment may increase due to a delay in the time to sputum conversion which will result in the extension of TB treatment beyond 6 months. Following treatment, participants will be followed up on a two-monthly basis for 12 months.

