##### Intention-to-treat population

This population consists of all participants enrolled and randomised to the intervention and control arms. Individuals who will be identified as ineligible for enrolment based on criteria pre-randomisation criteria will be excluded. Moreover, individuals with no post-randomisation visit and no data collected will be excluded.

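### Protocol 9.1 claims 80% power for 330 enrolled, but 330 is the number that must be evaluable; no loss is allowed for and the test is not named consistently

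*Protocol*

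**What the plan says.** Protocol 9.1 fixes enrolment ("A total of 330 patients will be enrolled") and states the design calculation: "A two group continuity corrected chi square test with a 0.05 two-sided significance level will have 80% power", for "75% of patients having culture conversion in the Intervention arm" against 60% in the control arm. It mentions no allowance for withdrawal, loss to follow-up or missing cultures. SAP section 2 gives 1:1 allocation and closes off any later increase: "A maximum of 330 participants will be included in the study".

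Several provisions elsewhere reduce the number of patients who can contribute an outcome:

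- Protocol 1.3 and 8.2.3 withdraw patients whose isolate proves multidrug resistant.
- The protocol's text on withdrawal from the study adds that "patients withdrawn from study because their initial cultures are negative do not need to be followed up further", apart from ongoing adverse events. Entry rests on smear and GeneXpert (4.1), and culture is first taken at baseline (Table 5), so a negative initial culture becomes known only after randomization.
- The SAP's intention-to-treat population leaves out patients found ineligible on pre-randomization criteria, and "individuals with no post-randomisation visit and no data collected will be excluded".
- SAP section 5 ignores missing data, treating them as missing at random, unless patterns suggest bias. It names no fallback rule.
- SAP 6.3 defines conversion by two negative cultures at different visits, so a missed culture can leave status undetermined.

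The test has three descriptions. Protocol 9.1 has a continuity-corrected chi-square. Protocol 9.2 plans "comparing these using the chi-square test" and is silent on correction. SAP 6.3 allows chi-square or Fisher's exact test, with no rule for choosing between them.

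**The concern.** A sample size section should give the power of the trial as it will be analysed. Here the enrolled number equals the evaluable number that the stated test needs, while other sections make some non-evaluable patients likely. Under the test named in 9.1, 80% is the figure for zero loss, and any loss takes power below it.

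The choice of test also moves the figure by about three percentage points at full enrolment, and the documents leave that choice open. If the primary comparison is not significant, readers will judge it against a stated 80%. They should be able to see how far the actual evaluable number and the actual test depart from that figure.

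**Working it through.** **Inputs.** Rates 0.75 and 0.60, two-sided 0.05, 80% power, 330 enrolled (Protocol 9.1); 1:1 allocation (SAP section 2), so 165 per arm. The loss rate is an assumption (0–20%), because the documents give none for the trial.

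**Reproducing the plan's figure.** With mean rate 0.675 and difference d = 0.15, the uncorrected number per arm is

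n₀ = [1.960·√(2·0.675·0.325) + 0.842·√(0.75·0.25 + 0.60·0.40)]² / 0.15²
= [1.960·0.6624 + 0.842·0.6538]² / 0.0225 = 151.9.

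The continuity-corrected number is

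n = (n₀/4)·[1 + √(1 + 4/(n₀·d))]² = (151.9/4)·(1 + 1.0842)² = 164.9.

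Rounded up, that is 165 per arm and 330 in total, an exact match. Without the correction it would be 152 per arm, or 304. So 330 is the corrected requirement with nothing added.

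**Power with fewer evaluable patients.** With m = 165·(1 − L) per arm, uncorrected power is

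Φ{[0.15·√m − 1.960·0.6624] / 0.6538}.

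For the corrected test, m is first replaced by (m·d − 1)²/(m·d²), which inverts the correction. At m = 165 this gives 151.9, as it should.

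| Assumed non-evaluable | Evaluable in total | Corrected chi-square | Uncorrected chi-square |
|---|---|---|---|
| 0% | 330 | 80.0% | 83.2% |
| 5% | 313.5 | 77.8% | 81.2% |
| 10% | 297 | 75.3% | 79.1% |
| 15% | 280.5 | 72.7% | 76.8% |
| 20% | 264 | 69.7% | 74.2% |

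The uncorrected test needs 304, so it keeps 80% up to (330 − 304)/330 = 7.9% loss, or 26 patients.

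**Cross-check by exact binomial enumeration.** At 330 evaluable: corrected 80.4%, uncorrected 83.5%, Fisher's exact 80.5%. Fisher's exact power is 78.0% at 314, about 76% at 298, 72.7% at 280 and 70.4% at 264. Fisher's test therefore tracks the corrected chi-square closely.

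**Sensitivity case only: missing counted as not converted.** Keeping 165 per arm and multiplying both rates by (1 − L), the uncorrected test has 77.2% power at 5%, 71.1% at 10% and 59.0% at 20%. SAP section 5 does not state this rule. Protocol 9.1 also supports its rates with cure-and-completion figures, which may already count non-completers as failures, so this calculation may count dropout twice.

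**The case against.** The strongest reply is that the continuity correction is itself a margin. It adds 26 patients to what an ordinary chi-square needs. If that is the test eventually run and missing values are dropped, as SAP section 5 says, power is 79.1% at 10% loss and 76.8% at 15%. On that reading the shortfall is about one to three points. This stands, and it limits the size of the point.

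A reader might infer that 80% holds only if all 330 are evaluable and a test outside the plan is applied. The documents do not support that. Complete evaluability is needed only under the corrected test or, in effect, Fisher's exact test, and the SAP allows the latter. Neither 9.2 nor SAP 6.3 says the chi-square is uncorrected. If it is, the mismatch between powered and analysed test works in the trial's favour and offsets attrition; it does not add to it.

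Three further cautions also stand:

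- The 12% in Protocol 1.1 is a national treatment-interruption rate on the WHO retreatment regimen. It is not a trial dropout rate and should not be used as one.
- GeneXpert screening for rifampicin resistance should keep withdrawals for multidrug resistance few.
- The withdrawal text governs follow-up. It does not say outright that withdrawn patients leave the primary denominator, so fewer than 330 evaluable is likely but not certain.

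None of this supplies an attrition allowance or settles which test and denominator apply.

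**Conclusion.** The point holds in a limited form. The 80% in Protocol 9.1 is arithmetically right for 330 evaluable patients and a continuity-corrected test. It is attached to 330 enrolled, without any allowance for loss and with enrolment capped at that number.

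At an assumed 10% to 20% non-evaluable, the shortfall from 80% is about 5 to 10 points under the corrected test or Fisher's exact test, and about 1 to 6 points under an uncorrected chi-square. Below about 8% loss the uncorrected test still meets 80%. These figures assume equal loss in both arms, unchanged rates of 75% and 60% among evaluable patients, and non-evaluable patients dropped from the comparison. Because the true loss rate, the test and the denominator are all unstated, the documents do not fix one power figure for the trial as it will be analysed. The larger drops seen when missing counts as not converted are not a property of the plan as written.

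**What to change.** Keep 330 enrolled, and change the wording in three places:

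1. Name one primary test in Protocol 9.1, Protocol 9.2 and SAP 6.3: corrected chi-square, uncorrected chi-square or Fisher's exact.
2. State the denominator of the primary comparison. Say whether patients withdrawn for multidrug resistance or negative initial cultures count in it, and how an undetermined conversion status is handled.
3. In 9.1, restate power for the named test as a short table over 0–20% non-evaluable, with the range labelled as an assumption. Show missing counted as not converted only as a labelled sensitivity case, with the caution that the planning rates may already include non-completers.

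The cost is a wording amendment to both documents. Enrolment and treatment do not change. The stated power may become slightly less favourable; if an uncorrected test is chosen and loss stays below about 8%, it will not fall below the present 80%.

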## **9.2 Analysis including statistical methods**

To answer the primary objective of this study the sputum culture conversion rates at the end of the intensive phase and at month 6 will be compared between the two treatment arms. This will be done by calculating the proportion of culture conversions in each of the two arms and comparing these using the chi-square test.

## **9.3 Explanation on how the results of this study will be used**

Many published reports have questioned the effectiveness of the standard WHO retreatment regimen and, more importantly the potential for amplification of TB drug resistance. Despite the enormous patient and public health cost of drug resistant TB, there has been a lack of research effort directed at investigating alternate regimens aimed at optimising treatment outcomes among retreatment patients who are most at risk of developing acquired drug resistant TB. This study proposes to use a regimen that omits an injectable agent, enhances time to culture conversion thereby shortening duration of treatment, increasing adherence and completion rates and reducing the likelihood of acquiring drug resistance. The availability of new generation rapid diagnostic technologies offers a unique opportunity of providing a targeted retreatment approach without compromising the efficacy of second line agents used to treat drug resistant TB. The goal of global tuberculosis research and control efforts to date has been the development of shorter TB treatment regimens. Investigating a retreatment regimen that can shorten duration of therapy is central to enhancing programmatic outcomes and this study is commensurate with this goal. Treatment default is associated with length of treatment, thus shortening treatment duration could improve outcomes, and reduce labour and financial implications of national TB control programs especially in countries with a high TB incidence. This study will explore an alternate retreatment regimen suitable for a national TB control program in a TB-HIV endemic setting.

## **10.0 HUMAN PARTICIPANTS**

### **10.1 Patient Recruitment**

Patients will be recruited from various health care facilities. Recruiters will be stationed within the TB facility and potential patients can be approached through several mechanisms:

HCT services – HIV testing and counselling is routinely offered at the PCZCDC which provides an ideal opportunity to conduct pre-screening

Each Health Care Facility has an in house National Health Laboratory Service. All new patients with a positive smear and GeneXpert Rifampicin sensitive can be identified at the laboratory and followed-up by a CAPRISA recruiter based at the facility. CAPRISA Recruiters can also identify patients with a past history of TB and the CAPRISA site can perform a GeneXpert and smear testing.

Clinic referrals - Clinicians or Professional Nurses at the facility will be trained on the study protocol and will refer patients for enrolment.

## 10.2 Ethics

Existing WHO and South African TB treatment guidelines recommend the provision of streptomycin as part of TB retreatment standard of care. However, both sets of guidelines are currently being revised, with WHO and the South African government indicating that streptomycin will no longer be recommended for TB retreatment in the next iteration of their respective guidelines (personal communications: [name], STOP TB working group; [name], SA National Director MDR TB). Some high TB burden countries have already successfully removed streptomycin from their NTP guidelines . This proposed study could provide the evidentiary basis for such a policy shift in South Africa and elsewhere.

## 10.3 Regulatory and ethical review

The study will be conducted under the oversight of the University of KwaZulu-Natal, Nelson R Mandela School of Medicine Biomedical Research Ethics Committee (BREC) and the South African Medicines Control Council (MCC). The study protocol will be submitted to the ethics committee and regulatory entities by the Principal Investigator and reviewed and approved by the ethics committee prior to study initiation. The investigator will provide progress reports and all other information required by the ethics committee/regulatory institutions to conduct its reviews. On approval of the study we will register the study with SANCTR (South African National Clinical Trials Register). We will also seek approval for the study from the eThekweni Municipality.

## 10.4 Informed consent process

Written informed consent will be obtained from each study participant prior to screening and enrolment (see Appendix I). Written informed consent will also be obtained for long-term specimen storage and possible future analyses. However, consent for specimen storage is not a pre-condition for study participation. Participants will be provided with a copy of their informed consent forms if they wish to receive them.

Study informed consent forms will describe the purpose of the study, the procedures to be followed, and the risks and benefits of participation. The informed consent forms will also be translated into *isiZulu* and the accuracy of the translation will be verified through independent back-translation.

The study consent process will include an assessment of each potential participant's understanding of the study and the risks and benefits of study participation, which are essential for an informed decision. Participants who are not able to demonstrate adequate understanding of key concepts will not be enrolled in the study.

## 10.5 Participant Confidentiality

All laboratory specimens, evaluation forms, reports, and other records that leave the site will be identified by coded number only to maintain participant confidentiality. All records will be kept locked. All computer entry and networking programs will be done with coded numbers only. Clinical information will not be released without written permission of the participant, except as necessary for monitoring by the ethics committee or the sponsor's designee. CAPRISA External monitors will also review clinical information. QA officers and Head of QA will not be on delegation of Authority Log as these staff serve as external monitors.

## **10.6 Good Clinical Practice**

The study will be carried out according to ICH-GCP and South African Good Clinical Practice Guidelines (SA GCP). The Principal Investigator and/or designee will ensure that the study staff are conducting the trial in accordance with SA GCP and ICH-GCP guidelines, ensure appropriate human subjects training for all study staff and safety of all trial participants. The study protocol and patient informed consents and all future revisions of these latter documents, will be reviewed and approved by the UKZN Biomedical Research Ethics Committee (UKZN BREC) and South African Medicines Control Council (MCC) prior to implementation. Quality control officers will perform daily quality checks on patient data and a Data manager will oversee the maintenance and completeness of the patient data.

All Serious Adverse Events (SAE's) will be reported to UKZN BREC and MCC within 7 business days of site awareness. A Safety Monitoring Committee (SMC) will meet annually to analyse and discuss safety data and make recommendations for the continuation of the trial and patient care.

## **11.0 DATA MANAGEMENT**

The entry, storage and cleaning of study data will be conducted under the oversight of the CAPRISA Data Management core.

### **11.1 Data Collection and Methods**

Case Report Forms (CRFs) will be provided for each patient. At screening participants will be issued a Screening Identification number (SID) by the site. At enrolment participants will be identified by a patient identification number (PID) provided by the CAPRISA Data Management Center. This PID is used on all CRFs to identify the participant for the duration of the study.

Data will be collected at scheduled clinic visits. Patients will be required to attend at the clinic for a screening visit and if found to be eligible, informed consent will be administered and the patient will be enrolled into the study. Post enrollment visits will be scheduled once a month for the Treatment phase of the study.

